**CONFIDENTIAL**

201214

ICH: Listings					
No.	Population	IDSL / Example Shell	Title	Programming Notes	Deliverable
13.	Safety	AE7	Listing of Subject Numbers for Individual Adverse Events	ICH E3	SAC
14.	Safety	AE2	Listing of Relationship Between Adverse Event System Organ Classes, Preferred Terms, and Verbatim Text	IDSL	SAC
Serious and Other Significant Adverse Events					
15.	Safety	AE8CP	Listing of Serious Adverse Events	ICH E3	SAC
16.	Safety	AE14	Listing of Reasons for Considering as a Serious Adverse Event	ICH E3	SAC
17.	Safety	AECP8	Listing of Adverse Events Leading to Withdrawal from Study / Permanent Discontinuation of Study Treatment	ICH E3	SAC
Hepatobiliary (Liver)					
18.	Safety	MH2	Listing of Medical Conditions for Subjects with Liver Stopping Events	IDSL	SAC
19.	Safety	SU2	Listing of Substance Use for Subjects with Liver Stopping Events	IDSL	SAC
All Laboratory					
20.	Safety	LB5	Listing of All Clinical Chemistry Data for Subjects with Any Value of Potential Clinical Importance	ICH E3 Display ALL chemistry data for a subject who experienced a value of potential clinical importance.	SAC
21.	Safety	LB5	Listing of Clinical Chemistry Values of Potential Clinical Importance		SAC
22.	Safety	LB5	Listing of All Hematology Data for Subjects with Any Value of Potential Clinical Importance	Display ALL hematology data for a subject who experienced a value of potential clinical importance.	SAC
23.	Safety	LB5	Listing of Hematology Values of Potential Clinical Importance		SAC

**CONFIDENTIAL**

201214

ICH: Listings					
No.	Population	IDSL / Example Shell	Title	Programming Notes	Deliverable
24.	Safety	LB14	Listing of Laboratory Data with Character Results	ICH E3	SAC
25.	Safety	UR2A	Listing of All Urinalysis Data for Subjects with Any Value of Potential Clinical Importance	ICH E3 Display ALL urinalysis data for a subject who experienced a value of potential clinical importance	SAC
ECG					
26.	Safety	EG3	Listing of All ECG Values for Subjects with Any Value of Potential Clinical Importance	IDSL Display ALL ECG data for a subject who experienced a value of potential clinical importance.	SAC
27.	Safety	EG3	Listing of ECG Values of Potential Clinical Importance	IDSL	SAC
28.	Safety	EG5	Listing of All ECG Findings for Subjects with an Abnormal ECG Finding	IDSL	SAC
29.	Safety	EG5	Listing of Abnormal ECG Findings	IDSL	SAC
Vital Signs					
30.	Safety	VS4	Listing of All Vital Signs Data for Subjects with Any Value of Potential Clinical Importance	IDSL Display ALL vital signs data for a subject who experienced a value of potential clinical importance.	SAC
31.	Safety	VS4	Listing of Vital Signs of Potential Clinical Importance	IDSL	SAC

**12.10.12. Non-ICH Listings**

Non-ICH: Listings					
No.	Population	IDSL / Example Shell	Title	Programming Notes	Deliverable
Protocol Deviation					
32.	Safety	DV2	Listing of All Non-Important COVID-19 Related Protocol Deviations		SAC
Adverse Events					
33.	Safety	PAN12	Listing of COVID-19 Assessments and Symptom Assessments for Subjects with COVID-19 Adverse Events		SAC
Pharmacokinetic					
34.	PK	PK07	Listing of Plasma Pharmacokinetic Concentration-Time Data		SAC
35.	PK	PK13	Listing of Derived Plasma Pharmacokinetic Parameters		SAC
Efficacy					
36.	Efficacy	Non-standard EFF_L1	Listing of Sputum Counts	Include CFU, log 10 CFU and TTP	SAC
37.	Safety	Non-standard EFF_L2	Listing of Mycobacterial Data		SAC
38.	Safety	Non-standard EFF_L3	Listing of Drug Susceptibility Data at Screening		SAC
All Laboratory					
39.	Safety	Non-standard SAFE_L1	Listing of Troponin Data		SAC

**12.11. Appendix 11: Example Mock Shells for Data Displays**

Example : EFF\_T1  
 Population : Efficacy

Table EFF\_T1  
 Summary Table of log10CFU Counts Over Time

Treatment	N	Planned Time	n	Mean	SD	Median	Min.	Max.
<Rifafour>	xx	Baseline	xx	x.xx	x.xxx	x.xx	x.x	x.x
		Day 1	xx	x.xx	x.xxx	x.xx	x.x	x.x
		Day 2	xx	x.xx	x.xxx	x.xx	x.x	x.x
		...	...	...	...	...	...	...
		Day 14	xx	x.xx	x.xxx	x.xx	x.x	x.x
<656 Dose 1>	xx	Baseline	xx	x.xx	x.xxx	x.xx	x.x	x.x
		Day 1	xx	x.xx	x.xxx	x.xx	x.x	x.x
		Day 2	xx	x.xx	x.xxx	x.xx	x.x	x.x
		...	...	...	...	...	...	...
		Day 14	xx	x.xx	x.xxx	x.xx	x.x	x.x
...								
<656 Dose 5>	xx	Baseline	xx	x.xx	x.xxx	x.xx	x.x	x.x
		Day 1	xx	x.xx	x.xxx	x.xx	x.x	x.x
		Day 2	xx	x.xx	x.xxx	x.xx	x.x	x.x
		...	...	...	...	...	...	...
		Day 14	xx	x.xx	x.xxx	x.xx	x.x	x.x

Baseline (Day 0) is defined as the mean of Day -2 and Day -1; if data was available at only one of these timepoints then that value was used as baseline. Where plate counts were Too Numerous To Count (TNTC), a value of 2500 was imputed for the analysis.

CONFIDENTIAL

201214

Example : EFF\_T2  
 Population : Efficacy

Table EFF\_T2  
 Rate of Change in log10CFU by Treatment - Mixed Model Analysis

Endpoint (units)	Treatment	N	n	Mean	SE	95% Confidence Interval
EBA CFU 0-14 (log 10 CFU/mL)	<Rifafour>	xx	xx	x.xx	x.xx	(x.xxx, x.xxx)
	<656 Dose 1>	xx	xx	x.xx	x.xx	(x.xxx, x.xxx)
	<656 Dose 2>	xx	xx	x.xx	x.xx	(x.xxx, x.xxx)
	<656 Dose 3>	xx	xx	x.xx	x.xx	(x.xxx, x.xxx)
	<656 Dose 4>	xx	xx	x.xx	x.xx	(x.xxx, x.xxx)
	<656 Dose 5>	xx	xx	x.xx	x.xx	(x.xxx, x.xxx)
EBA CFU 0-2 (log 10 CFU/mL)	<Rifafour>	xx	xx	x.xx	x.xx	(x.xxx, x.xxx)
	<656 Dose 1>	xx	xx	x.xx	x.xx	(x.xxx, x.xxx)
	<656 Dose 2>	xx	xx	x.xx	x.xx	(x.xxx, x.xxx)
	<656 Dose 3>	xx	xx	x.xx	x.xx	(x.xxx, x.xxx)
	<656 Dose 4>	xx	xx	x.xx	x.xx	(x.xxx, x.xxx)
EBA CFU 2-14 (log 10 CFU/mL)	<Rifafour>	xx	xx	x.xx	x.xx	(x.xxx, x.xxx)
	<656 Dose 1>	xx	xx	x.xx	x.xx	(x.xxx, x.xxx)
	<656 Dose 2>	xx	xx	x.xx	x.xx	(x.xxx, x.xxx)
	<656 Dose 3>	xx	xx	x.xx	x.xx	(x.xxx, x.xxx)
	<656 Dose 4>	xx	xx	x.xx	x.xx	(x.xxx, x.xxx)
	<656 Dose 5>	xx	xx	x.xx	x.xx	(x.xxx, x.xxx)

Mixed model including treatment, day,, BMI and treatment-by-day as covariates. The Day 2-14 model also includes log baseline CFU as a covariate. Baseline (Day 0) is defined as the mean of Day -2 and Day -1; if data was available at only one of these timepoints then that value was used as baseline.

Example : EFF\_T3  
 Population : Efficacy

Table EFF\_T3  
 Node and Slope Parameter Estimates for log10CFU by Treatment - Bi-linear Bayesian Model Analysis

Endpoint (units)	Treatment	N	n	Mean (95% HPD Interval)		
				Node	Slope Before Node	Slope After Node
EBA CFU 0-14 (log 10 CFU/mL)	<Rifafour>	xx	xx	x.xxx (x.xxx, x.xxx)	x.xxx (x.xxx, x.xxx)	x.xxx (x.xxx, x.xxx)
	<656 Dose 1>	xx	xx	x.xxx (x.xxx, x.xxx)	x.xxx (x.xxx, x.xxx)	x.xxx (x.xxx, x.xxx)
	<656 Dose 2>	xx	xx	x.xxx (x.xxx, x.xxx)	x.xxx (x.xxx, x.xxx)	x.xxx (x.xxx, x.xxx)
	<656 Dose ...>	xx	xx	x.xxx (x.xxx, x.xxx)	x.xxx (x.xxx, x.xxx)	x.xxx (x.xxx, x.xxx)
	<656 Dose 5>	xx	xx	x.xxx (x.xxx, x.xxx)	x.xxx (x.xxx, x.xxx)	x.xxx (x.xxx, x.xxx)
EBA CFU 2-14 (log 10 CFU/mL)	<Rifafour>	xx	xx	x.xxx (x.xxx, x.xxx)	x.xxx (x.xxx, x.xxx)	x.xxx (x.xxx, x.xxx)
	<656 Dose 1>	xx	xx	x.xxx (x.xxx, x.xxx)	x.xxx (x.xxx, x.xxx)	x.xxx (x.xxx, x.xxx)
	<656 Dose 2>	xx	xx	x.xxx (x.xxx, x.xxx)	x.xxx (x.xxx, x.xxx)	x.xxx (x.xxx, x.xxx)
	<656 Dose ...>	xx	xx	x.xxx (x.xxx, x.xxx)	x.xxx (x.xxx, x.xxx)	x.xxx (x.xxx, x.xxx)
	<656 Dose 5>	xx	xx	x.xxx (x.xxx, x.xxx)	x.xxx (x.xxx, x.xxx)	x.xxx (x.xxx, x.xxx)

Bi-linear model including treatment, day, BMI and treatment-by-day before node and treatment-by-day after node as covariates. The Day 2-14 model also includes log baseline CFU as a covariate. Baseline (Day 0) is defined as the mean of Day -2 and Day -1; if data was available at only one of these timepoints then that value was used as baseline.

Example : EFF\_T4  
 Population : Efficacy

Table EFF\_T4  
 Summary of Covariate and Treatment\*Covariate Interaction Significance For log10CFU (0-14) Mixed Model Analysis

Terms in the Model	Numerator Degrees of Freedom	Denominator Degrees of Freedom	F-test	p-value
Age [1]	xx	xx	x.xx	0.xxx
Treatment*Age [1]	xx	xx	x.xx	0.xxx
Creatinine clearance [2]	xx	xx	x.xx	0.xxx
Treatment*creatinine clearance [2]	xx	xx	x.xx	0.xxx
...				

Primary model includes treatment, day, BMI and treatment-by-day as covariates.

[figure not shown]
[1] Primary model fitted first with age, then with age + age\*treatment

[2] Primary model fitted first with creatinine clearance, then with creatinine clearance creatinine clearance\*treatment

...

Example : EFF\_F1  
Population : Efficacy

Table EFF\_F1  
Line Graph of Mean log10CFU Over Time by Treatment

[figure not shown]

Programming note: Include 95% confidence intervals of the slopes.

Example : EFF\_F2  
Population : Efficacy

[figure not shown]
Table EFF\_F2  
Individual Subject Profile Plots of log10(CFU) Count Over Time by Treatment

Programming notes: Produce separate figure per treatment group.

Example : EFF\_F3  
Population : Efficacy

Table EFF\_F3  
Line Graph of Dose vs  $\log_{10}CFU(0-14)$  Slope

Programming note: Include 95% HPD interval of the slopes.

CONFIDENTIAL

201214

Example : PK\_T1  
Population : Pharmacokinetic

Table PK\_T1  
Statistical Analysis of Log Transformed Plasma GSK3036656 Pharmacokinetic Parameters Assessing Dose Proportionality (Power Model)

Parameter (Units)	Timepoint	Slope Log Parameter vs Log Dose	90% CI of the Slope
<AUC(0-t) (µg.h/mL)>	Day 14	x.xx	(x.xx, x.xx)
Cmax (µg/mL)	Day 14	x.xx	(x.xx, x.xx)

Log(dose) is fitted as a fixed effect.  
A slope of 1 indicates the pharmacokinetics are dose proportional. A slope greater than 1 indicates the increase in PK is greater than proportional to dose.

Example : PK\_T2  
 Population : Pharmacokinetic

Table PK\_T2

Statistical Analysis of log transformed plasma GSK3036656 Trough Concentration Assessing Steady State

Parameter (Units)	Treatment	Day*	Back-Transformed Slope	90% Confidence Interval
Ctau (ng/mL)	<656 Dose 1>	12-14	x.xx	(x.xx, x.xx)
	<656 Dose 2>	12-14	x.xx	(x.xx, x.xx)
	<656 Dose 3>	12-14	x.xx	(x.xx, x.xx)
	<656 Dose 4>	12-14	x.xx	(x.xx, x.xx)
	<656 Dose 5>	12-14	x.xx	(x.xx, x.xx)

Mixed effect model including log(dose), day and log(dose)-by-day interaction as fixed effects and subject as a random effect. An unstructured covariance structure was used.

[figure not shown]
A slope of 1 indicates steady state.

\*Day 14 includes the Day 14 24 hour PK sample.

Example : PK\_F1  
Population : Pharmacokinetic

Figure PK\_F2

Scatterplot of Dose vs AUC(0-inf) including Regression Line - Part A

CONFIDENTIAL

201214

Example : EFF\_L1  
Population : Efficacy

Table EFF\_L1

Listing of Sputum Counts

Site ID: <11111>

Treatment / Unique subject Id. / Subject Id.	Age (Years)/ Sex/ Race Detail	DateTime / Study Day	CFU (CFU/mL)	Log10CFU (log10CFU/mL)	TTP (hours)
xxxxxx / xxxxxx / xxxxx	xx / <M/F> / xxxxxx	YYYY-MM- DDTHH:MM / xx YYYY-MM- DDTHH:MM / xx	x.xxx  x.xxx	x.xxx  x.xxx	x.xxx  x.xxx

Note, mean values at each timepoint are displayed.

CONFIDENTIAL

201214

Example : EFF\_L2  
Population : Safety

Table EFF\_L2  
Listing of Mycobacterial Data

Site Id.: <1111111>

Treatment / Unique subject Id. / Subject Id.	Age (Years) / Sex / Race Detail	Microscopy Collection Date / Time	Microscopy Result / Grading	GeneXpert Collection Date / Time	GeneXpert Result at baseline	GeneXpert Positive Rating at baseline
xxxxxx / xxxxxx / xxxxx	xx / <M/F> / xxxxx	XXXXXX /HH:MM	< Positive / No AFB seen / No result / Not done> / < Scanty / 1+ / 2+ / 3+ / N/A>	XXXXXX /HH:MM	<MTB NOT DETECTED / MTB DETECTED; Rif Resistance NOT DETECTED / MTB DETECTED; Rif Resistance DETECTED / MTB DETECTED; Rif Resistance INDETERMINATE / Invalid / Error / No result>	<High positive / Medium positive / Low positive / Very low positive / N/A>

...

Footnote: Note, Grading is presented as: 1=1+, 2=2+, 3=3+, 4=4+  
Programmers note: For repeat results, display all available results, one row per repeat.

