	
Calculations will be based on the actual sampling times recorded during the study.
 
From the plasma concentration-time data, the following pharmacokinetic parameters will be determined, as data permit:
 
 
• maximum observed blood concentration (Cmax)
 
• time to Cmax (tmax)
 
• area under the plasma concentration-time curve [AUC0-t and AUC0-24]
 
• trough concentration (Cτ).
 
 
AUC0-t or AUC0-24 and Cmax may be used for assessment of dose proportionality. Trough concentration (Cτ) samples collected on the specified days will be used to assess attainment of steady state.
 
Pharmacokinetic data will be presented in graphical and/or tabular form and will be summarized descriptively.
 
Statistical analyses of the pharmacokinetic parameter data will be the responsibility of Statistics, Programming and Data Strategy (SPDS), GlaxoSmithKline. Distributional assumptions underlying the statistical analyses will be assessed by visual inspection of residual plots. Normality will be examined by normal probability plots, while homogeneity of variance will be assessed by plotting the residuals against the predicted values for the model. Alternative analyses of the data will be performed if any of the model assumptions appear to be violated. Full details on the statistical aspects will be detailed in the Reporting and Analysis Plan (RAP).
 
Dose Proportionality
 
Dose proportionality will be assessed via analyses of AUC0-t or AUC0-24 and Cmax. A statistical analysis will be performed using the power model. The analysis will be performed on loge-transformed data. For each of these parameters a mixed effects model will be fitted with loge (dose) as a fixed effect and individual subject fitted as random effects. Estimates of the mean slopes of loge (dose) will be reported along with corresponding 90% confidence intervals (slope≈1 implies dose proportionality).
 
Achievement of Steady State
 
Trough concentration levels, Cτ, collected pre-morning dose will be plotted by collection day and dose. To evaluate whether steady state was achieved, statistical analysis of Cτ will be performed after a log-transformation of the dose data. A mixed effect model will be fitted with dose, day and dose-by-day interaction as fixed effects (with dose as a factor and day as a continuous covariate) and subject as a random effect. The coefficients of the

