Random effect: participant

Day will be treated as a continuous variable, dose as a categorical variable.

- The dose-by-day interaction will be tested for its significance at the 5% level, if the interaction is not significant then a single point estimate for all dose levels pooled will be calculated in addition to the individual dose levels.
- The Kenward Roger method for approximating the denominator degrees of freedom and correcting for bias in the estimated variance-covariance of the fixed effects will be used.
- An unstructured (UN) covariance structure for the G matrix will be used.
  - In the event that this model fails to converge, alternative covariance structures may be considered such as variance components (VC) or compound symmetry (CS).
  - Akaike's Information Criteria (AIC) will be used to assist with the selection of covariance structure.

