### Model Results Presentation

- The coefficients of the slopes for the day effect for each dose, along with corresponding 90% confidence intervals, will be used to determine whether steady state was achieved.
- If the interaction is not significant, then a single point estimate and corresponding 90% confidence interval for all dose levels pooled will be presented.
- Trough concentration levels collected pre-morning dose will be plotted by collection day and dose.

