- b. Participants can proceed with the Visit 2 (day -2) assessments as soon as their Visit 1 (day -9 to -3) assessments have been completed i.e. Visits 1 and 2 may occur on the same day as long as the screening results are available in time for randomisation. Participants may be hospitalised during the entire pre-treatment period if the Investigator considers it advisable for reasons of safety or compliance.
- c. All events listed as occurring on Visit 5 (day 2) to Visit 10 (day 7) and Visit 12 (day 9) to Visit 16 (day 13) will be conducted each day during these visits.
- d. Height (m) will only be collected once at Visit 1 (day -9 to -3). A full physical examination will be performed at Visit 1 (day -9 to -3), with symptom-directed physical examinations at Visit 17 (day 14), Visit 19 (day 28) and Early Withdrawal Visit (EWV). Symptom directed physical examinations may be conducted as required during the study (visits 4 to 16). Requirements for the physical examination are specified in the SRM.
- e. Systolic blood pressure (SBP) and diastolic blood pressure (DBP) (mmHg), heart rate (beats per minute [bpm]), body temperature (°C), respiratory rate (breathes per minute) and weight (kg). To be performed within 4 hours prior to the first daily dosing on Visit 4 (day 1) through to Visit 17 (day 14) and within 4 hours before the time dosing would have occurred on Visit 18 (day 15). On days where the following assessments are done the order should be: vital signs before blood draws for PK or safety assessments.
- f. PKs will be performed as noted in the PK table. A single pre-dose PK sample will be collected on each of Days 12 & 13, and serial PK blood sampling will occur on Day 14 (see PK table below). At EWV a PK sample will be taken before the time of the planned daily dosing. If this is not possible, a spontaneous PK sample will be taken.
- g. Sputum smear microscopy and molecular rapid test for confirmation of Mycobacterium tuberculosis and rifampicin susceptibility (GeneXpert). If the first spot sputum or overnight sputum sample shows an unfavourable result, the tests may be repeated on a freshly collected spot sputum or overnight sputum sample and that result used instead.
- h. Refer to [Appendix 3](#) for details.
- i. Urine drug screen: cocaine, amphetamines and opiates. Urine drug screen can be repeated at Visit 2 (day -2) for participants who were not hospitalized at Visit 1 (day -9 to -3).
- j. **CCI**
- k. 

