**PK sampling time and events table**

STUDY VISIT	Visit 15	Visit 16	Visit 17										Visit 18
STUDY DAY	Day 12	Day 13	Day 14										Day 15
STUDY HOUR B			0	0.5	1	1.5	2	3	4	6	8	12	24
Pharmacokinetic sampling C	X A	X A	X D	X	X	X	X	X	X	X	X	X	X

- A. Sample to be taken within 30 minutes pre-dose.
- B. All values are relative to the time of day that the study treatment is administered on Day 14.
- C. PK sampling is only to be performed on participants receiving GSK3036656. PK samples will not be taken from participants receiving Rifafour e-275 (or equivalent generic alternative).
- D. Sample to be taken within 10 minutes pre-dose

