## 12.10.10. Pharmacokinetic Figures

Pharmacokinetic: Figures					
No.	Population	IDSL / Example Shell	Title	Programming Notes	Deliverable
Pharmacokinetic Concentration Data					
4.1.	PK	PK16a	Individual Plasma GSK3036656 Concentration-Time Plot (Linear and Semi-Log) by Subject		SAC
4.2.	PK	PK24	Individual Plasma GSK3036656 Concentration-Time Plot (Linear and Semi-Log) by Treatment	Include Day 14 and 15 data only.	SAC
4.3.	PK	PK17	Mean Plasma GSK3036656 Concentration-Time Plots (Linear and Semi-Log)	Include Day 14 and 15 data only.	SAC
4.4.	PK	PK18	Median Plasma GSK3036656 Concentration-Time Plots (Linear and Semi-Log)	Include Day 14 and 15 data only.	SAC
Derived Pharmacokinetic Parameters					
4.5.	PK	PK25	Comparative Plot of Individual Subject Plasma GSK3036656 Pharmacokinetic Parameter By Treatment	Ct	SAC
4.6.	PK	Non-standard PK_F1	Scatterplot of log(dose) vs log(AUC)	Add footnote: Doses displayed on the log scale are Xmg, Xmg, Xmg and Xmg.	SAC
4.7.	PK	Non-standard PK_F1	Scatterplot of log(dose) vs log(Cmax)	Add footnote: Doses displayed on the log scale are Xmg, Xmg, Xmg and Xmg.	SAC

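### Shell PK_T2 labels the 24-hour trough as Day 14 although the rest of the SAP places it on Day 15; programmed as written, the steady-state slope is mis-scaled and its CI is too wide

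*SAP*

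**What the plan says.** **The model.** SAP 9.1.5.1 (Achievement of Steady State) fits a mixed model to trough concentration with dose, day and their interaction as fixed effects. It states "Day will be treated as a continuous variable, dose as a categorical variable" and "Random effect: participant". Protocol 10.3.1 describes the same model. Both documents judge steady state from the day slope for each dose and its 90% CI. Shell PK_T2 presents the slope back-transformed and notes that a value of 1 indicates steady state.

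**The samples.** SAP Appendix 2 states: "A single pre-dose PK sample will be collected on each of Days 12 & 13, and serial PK blood sampling will occur on Day 14". The Day 14 series begins with a pre-dose (0 h) sample and ends 24 h after dosing. There are therefore four candidate troughs per participant: pre-dose on Days 12, 13 and 14, and 24 h after the Day 14 dose.

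**The day given to the fourth trough.**
- Shell PK_T2 prints the range 12-14 with the footnote "Day 14 includes the Day 14 24 hour PK sample".
- The PK sampling table in SAP Appendix 2 puts the 24 h sample at Visit 18, Day 15.
- SAP 12.3.1 gives Day 15 its own PK window.
- The Study Day rule in SAP 12.6.1 (date minus first dose date, plus 1) yields 15.
- The concentration-time figures in SAP 12.10.10 carry the note "Include Day 14 and 15 data only", so they name the two days separately.

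SAP 9.1.5.1 gives no numeric day for this sample. For this analysis, the shell footnote is the only text that does.

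**The concern.** The Day 14 pre-dose and 24-hour troughs are one dosing interval apart. In a regression on continuous day, the number attached to each sample determines both the slope and its standard error. Giving both samples the value 14 compresses the time axis. A drift that took three days to build up is divided by a shorter apparent span, and the longest time contrast in the data is lost.

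The label also opens a second question. Two values that share a day could be taken as duplicates under SAP 12.6.1, which has one rule that averages multiple measurements and another that keeps the earliest value in a window. A programmer working from the footnote could therefore reach three different answers. What is at stake is the accuracy and precision of the slope that the SAP names as its basis for judging steady state.

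**Working it through.** Neither document gives a precision or power figure for this slope, so there is no stated figure to reproduce.

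**Inputs.** True days t = 12, 13, 14, 15 (PK sampling table). Coded days x = 12, 13, 14, 14 (shell footnote). Random participant intercept only (SAP 9.1.5.1). Assumed for the check: complete data, independent residuals with variance s², and drift that is constant per day on the log scale. The slope is then the within-participant least-squares slope, with variance proportional to 1/Sxx.

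**Two Day 14 records (footnote as it reads)**
- True coding: mean 13.5, Sxx = 2.25 + 0.25 + 0.25 + 2.25 = 5.00.
- Footnote coding: mean 13.25, Sxx = 1.5625 + 0.0625 + 0.5625 + 0.5625 = 2.75.
- Cross-product: Sxy = (-1.25)(12) + (-0.25)(13) + (0.75)(14) + (0.75)(15) = 3.5.
- Expected slope = 3.5/2.75 = 1.27 times the true drift.
- SE and log-scale CI width ratio = sqrt(5.00/2.75) = 1.35.
- Information kept = 2.75/5.00 = 55%. An arm of 9 (Protocol 10.1.2) has the slope precision of about 9 × 0.55 = 5 participants.
- Slope/SE changes by 1.273/1.348 = 0.94, a fall of about 6%.

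**Duplicate rules applied instead**
- Mean of the two: the last point is coded 14 but represents day 14.5. Slope factor = (14.5 - 12)/2 = 1.25. Variance = s²(1/4 + 1/8) = 0.375 s², against s²/5 = 0.20 s² with true days. SE ratio = sqrt(0.375/0.20) = 1.37.
- Earliest value: the 24 h sample drops out. Slope factor = 1.00. Sxx = 2, so SE ratio = sqrt(5/2) = 1.58.

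| Handling of the 24 h trough | Slope factor | CI width ratio |
|---|---|---|
| Day 15, own record | 1.00 | 1.00 |
| Day 14, two records | 1.27 | 1.35 |
| Day 14, mean of the two | 1.25 | 1.37 |
| Day 14, earliest kept | 1.00 | 1.58 |

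**Checks on the two-record case**
- Mixed-model simulation: 150 data sets at each of two drifts, n = 15, with assumed log-scale SDs of 0.30 between and 0.12 within participants. The SE ratio was 1.347 with no drift and 1.373 with a drift of 0.05 per day. The slope ratio at that drift was 1.270.
- AR(1) residuals with correlation 0.3 to 0.7: CI 32-34% wider.
- Random slope added, with variance 0.1 to 1 times the residual variance: CI 29-32% wider.
- Back-transformed scale, drift of 0.01 to 0.10 per day on the log scale: inflation 27-29%.
- Curved approach to steady state with the 45-hour half-life in Protocol 5.6: inflation about 34%.

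**The case against.** **The coding is inferred from a mock table.** The footnote may mean only that the 24-hour sample, as the end of the Day 14 profile, is included in the analysis. The windows in SAP 12.3.1 and the Study Day rule point to Day 15, and a programmer who follows them would see neither effect. This stands, and it is why the sizes above are conditional. The table would still be mislabelled, so the text needs correcting in either case.

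**The absolute error is small.** Assume a one-compartment model with the 45-hour half-life. With no loading dose, drift over Days 12 to 15 is about 0.39% per day and would be reported as about 0.52%. With the 15 mg/5 mg regimen it is about 0.04% against 0.05%. Protocol 5.6 expects a loading dose to bring steady state within 2 to 3 days. This stands for the bias. It does not answer the loss of precision, which occurs at any drift, including zero.

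**The coding might be thought to make steady state easier to claim.** A reader might infer this from the wider CI, but the documents do not support it. The SAP says that the slope and its CI will be used but gives no decision rule or margin. If the rule were that the CI includes 1, the change in slope/SE is only about 6% in the two-record case. Under an equivalence-type rule, a wider CI would make the claim harder.

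**Deleting the footnote would do harm.** Both documents describe the plotted troughs as taken before the morning dose, and no study dose is given on Day 15. The footnote is the only explicit statement that the 24-hour sample enters this analysis. This stands, and the fix keeps a footnote.

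**Conclusion.** The shell conflicts with the SAP's own sampling table, analysis windows and Study Day rule, and should be corrected. Programmed as the footnote reads, with two Day 14 records per participant, it gives a 90% CI about 35% wider than needed and overstates a constant log-linear drift by about 27%. The duplicate rules would give 25% and 37% wider (mean), or no inflation and 58% wider (earliest value). These figures assume a random intercept, complete data and independent residuals.

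The finding has limits. It does not show that the analysis will in fact be run on Day 14 coding, because the model section is silent. It does not show that every drift is inflated by 27%: that figure is for constant drift, and a curved approach gives about 34%. With zero drift the slope is unbiased and only the CI suffers. A reader might also suppose that dose escalation or the primary endpoint is affected. Neither is: Protocol Section 11 bases PK-driven escalation on modelled AUC and Cmax against exposure limits, and the primary endpoint uses sputum counts. This is a low-priority correction to a secondary PK analysis.

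**What to change.** 1. In SAP 9.1.5.1, state that the trough taken 24 hours after the Day 14 dose enters the steady-state model as its own record with day = 15. The duplicate rules in SAP 12.6.1 then do not arise.
2. In shell PK_T2, change the day range to 12-15.
3. Reword the footnote to say that Day 15 is the 24-hour sample after the Day 14 dose. Do not delete it.

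The cost is one sentence, one line of code and one shell edit. No new data are needed.
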